Conventional treatment includes wait and see approach for asymptomatic patients, erythropoiesis-stimulating agents, androgens or immunomodulatory agents for anemia, cytoreductive drugs such as hydroxyurea for splenomegaly and constitutional symptoms, and splenectomy or radiotherapy for selected patients.²⁰ Currently, ruxolitinib, a dual JAK-1 and -2 inhibitor, is the only targeted therapy approved for the treatment of myelofibrosis in the United States and European Union. While the approval of ruxolitinib has changed the treatment landscape for patients with myelofibrosis, it is still aimed at improving symptoms and quality of life. The only treatment modality capable of curing MF is allogenic HSCT. The applicability of HSCT is limited by the inherent risks in this population, with their attendant comorbidities.

Fedratinib, a JAK-2 specific inhibitor, is currently in clinical development and has been evaluated in patients with MF. The reported SVR₃₅ with fedratinib in the previously untreated population is similar that reported of ruxolitinib at approximately 40%. ^{21,22} A recent re-analysis of the JAKARTA-2 study of fedratinib in patients with MF that previously failed ruxolitinib treatment reports a SVR₃₅ of 30%. The most common adverse events in the JAKARTA-2 study in the ruxolitinib failure cohort are reported as anemia (100%), platelet count decrease (73%), creatinine increased (72%), diarrhea (65%), nausea (53%), and ALT increased (52%). Additionally, among the 600 subjects treated with fedratinib in clinical trials, 8 subjects were reported to have potential Wernicke's encephalopathy.²³

Navitoclax has been evaluated in 25 clinical studies as both single-agent and as combination therapy. Clinical studies have assessed the safety, pharmacokinetics and initial efficacy in subjects with hematologic malignancies or in subject with solid tumors. There is preclinical data that suggest that the combination of navitoclax with ruxolitinib may provide disease-modifying therapy for patients with PMF or SMF.

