- Treatment with NSAIDs for limited duration are permitted during study treatment if the platelet counts $> 100 \times 10^9$ /L.

Anti-cancer therapy including chemotherapy, cytoreductive agents, immunotherapy, radiotherapy, hormonal (with the exception of hormones for thyroid conditions or estrogen replacement therapy), and other investigational agents will not be allowed during study treatment. Hydroxyurea should be discontinued at least 7 days before initiation of navitoclax on Day 1.

Treatment with supportive medications for MF such as interferon, erythropoietin, danazol, and steroids, is not permitted during study drug treatment. Steroid therapy for MF or for anti-neoplastic intent will not be allowed within 7 days prior to the first dose of study treatment or during study drug treatment. If medically indicated, allowed steroid therapy includes inhalational steroids for the treatment of asthma or chronic obstructive pulmonary disease, topical steroids, and steroids for prevention and/or treatment of transfusion related reactions. Steroids for any other indications should be limited to lower dose and /or short duration.

For subjects in Cohort 2 receiving treatment with JAK-2 inhibitor therapy prior to study enrollment, a wash-out period is not required. The last dose of the JAK-2 inhibitor therapy must occur ≥ 1 day prior to Day 1 (first dose of navitoclax).

[figure not shown]
Biologics for MF will not be allowed within 30 days prior to the first dose of study drug and during navitoclax administration.

Colony stimulating factors (G-CSF, GM-CSF) may be considered during administration of navitoclax if deemed necessary by the investigator.

If clinically indicated, anti-herpes and anti-PCP (Pneumocystis carinii/jiroveci pneumonia) prophylaxis should be considered. Although there is a potential for drugdrug interactions trimethoprim sulfamethoxazole can be considered for PCP prophylaxis with close clinical monitoring.

COVID-19 Pandemic-Related Vaccination Guidance

Given the ongoing COVID-19 pandemic, selected non-live vaccines (e.g., mRNA, non-replicating viral vector, protein subunit, etc.) to prevent SARS-CoV-2 infection may be administered during screening or the treatment period, as long as components of the vaccine are not contraindicated. Investigators are to follow the prescribing information for the vaccine.

M16-109 Protocol Amendment 11 EudraCT 2017-001398-17

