^{**} Transfusion dependency before study enrollment is defined as transfusions of at least 6 units of packed red blood cells (PRBC), in the 12 weeks prior to study enrollment. In addition, the most recent transfusion episode must have occurred in the 28 days prior to study enrollment. Response in transfusion-dependent patients requires absence of any PRBC transfusions during any consecutive "rolling" 12-week interval during the treatment phase.

^{***} Requires confirmation by MRI/CT with a \geq 35% SVR.

[figure not shown]

Table 10. Summary of Cytogenetic Remission

Cytogenetic Remission Category	Cytogenetic Remission Requirements At least 10 metaphases must be analyzed
	Requires confirmation by repeat testing within 6 months
Complete Cytogenetic Remission	Eradication of a preexisting abnormality
Partial Cytogenetic Remission	\geq 50% reduction in abnormal metaphases (to qualify for PR: must have \geq 10 abnormal metaphases at baseline)

Table 11. Summary of Molecular Remission

Molecular Remission	Molecular Remission Requirements		
Category	Must be analyzed in peripheral blood granulocytes		
	Requires confirmation by repeat testing within 6 months		
Complete Molecular Remission	Eradication of a pre-existing abnormality		
Partial Molecular Remission	\geq 50% decrease in allele burden (to qualify for PR: must have \geq 20% mutant allele burden at baseling		

[figure not shown]

Table 12. Summary of Progression/Relapse Criteria

Progression/Relapse Category	Progression/Relapse Criteria		
Progressive Disease	At least 1 of the following:		
	• Appearance of a new splenomegaly that is palpable at least 5 cm below the left costal margin (LCM)*		
	• A \geq 100% increase in palpable distance below LCM, for baseline splenomegaly of 5 – 10 cm*		
	• A 50% increase in palpable distance below LCM, for baseline splenomegaly of > 10 cm*		
	• MRI/CT showing a \geq 25% increase in spleen volume from baseline		
	• Leukemic transformation confirmed by a bone marrow blast count of ≥ 20%		
	• A peripheral blood blast content of $\geq 20\%$ associated with an absolute blast count of $\geq 1 \times 10^9/L$ that lasts for at least 2 weeks		
Relapse	At least 1 of the following:		
	No longer meeting criteria for at least Clinical Improvement after achieving Complete Response, Partial Response or Clinical Improvement		
	• Loss of anemia response persisting for ≥ 1 month		
	• Loss of spleen response persisting for ≥ 1 month		

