#### 8.4.1.2 Anemia Response

Anemia response rate is defined as the proportion of subjects who achieved anemia response.

Baseline hemoglobin mentioned below is defined in Section 7.2.2. The transfusion dependency status (transfusion independent and transfusion dependent) mentioned below

are based on investigators reporting in the Study Cancer History Form according PRBC transfusion events ( $\geq 6$  units within 12 weeks and  $\geq 1$  unit within 28 days) prior to the start of study treatment.

For a subject who is transfusion independent (TI) at baseline with hemoglobin value < 10 g/dL, the subject will be considered as achieving anemia response if the post baseline hemoglobin level increases by  $\ge 2 \text{ g/dL}$  from baseline without receiving PRBC transfusion (for any reason) within 2 weeks and without any erythropoietin, erythropoietin mimetics within the last 4 weeks prior to the increase in hemoglobin level by  $\ge 2 \text{g/dL}$  was observed. Hemoglobin values after 30 days post last date of study treatment, the start of post-study treatment or disease progression whichever is earlier will not be considered in the analysis of anemia response.

For a subject who is transfusion dependent (TD) at baseline, anemia response is defined as a period of at least 12 consecutive weeks without PRBC transfusion after the first dose of study drug and on or prior to 30 days post last dose of study drug, the start of post-study treatment, disease progression or death, whichever occurs earlier.

[figure not shown]
Subjects who are baseline transfusion independent with baseline hemoglobin of  $\geq 10$  g/dL will not be included in the analysis since these subjects are not evaluable for anemia response.

Anemia response rate will also be summarized for all subjects who are evaluable for anemia response in the Full Analysis Set and by transfusion dependency status at baseline.

Missing post-baseline anemia response in Full Analysis Set applicable to evaluation of anemia response are considered as non-responders of anemia response.

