#### 8.5.1.7 Duration of Anemia Response

Duration of anemia response will be summarized by baseline transfusion status.

For subjects who were transfusion independent at baseline and achieved anemia response, the evaluation period for duration of anemia response is from achieving anemia response to 30 days after last dose of study treatment. Duration of anemia response is defined as number of days from the first date of achieving anemia response described in Table 6 to the date of loss anemia response as described in Table 7.

Table 6. Date of First Anemia Response for Duration of Anemia Response

Transfusion Status at baseline	Date of First Response
TI	On the first date observing hemoglobin level increase by $\geq 2$ g/dL from baseline without receiving PRBC transfusion within the last 2 weeks or any erythropoietin, erythropoietin mimetics within 4 weeks prior to the increased hemoglobin level
TD	On the first date observing no PRBC transfusion for at least 12 weeks

Table 7. Event and Censoring Condition for Duration of Anemia Response

[figure not shown]
Transfusion Status at baseline	Event/Censor	Date of Event/Censor
TI	Event: 1) decrease in hemoglobin level by 2 g/dL or more from the hemoglobin level at the first occurrence of achieving anemia response, or 2) need for PRBC transfusion before disease progression for the bleeding event* which was unrelated to navitoclax/ruxolitinib or 3) use of any erythropoietin, erythropoietin mimetics within 30 days of last dose of study drug	Earliest date of events
	Censor: if no above-mentioned events observed within 30 days of last dose of study drug	The last date of hemoglobin assessment after achieving anemia response, 30 days post last dose of study treatment, start of post-study treatment, disease progression, or death, whichever is earlier.  Date of achieving anemia response will be the censor date if no hemoglobin assessment is obtained after achieving anemia response.

\* Bleeding event is defined as a treatment emergent hemorrhage event from narrow search of Standardized MedDRA Queries (SMQ). PRBC occurring between the start of bleeding event and end/ongoing will be considered as need for PRBC transfusion for bleeding.

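### Erythropoietin use disqualifies an anemia response in transfusion-independent subjects but not in transfusion-dependent subjects, and the two groups are combined in one rate

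*SAP*

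**What the plan says.** SAP 8.4.1.2 defines anemia response separately by baseline transfusion status.

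- **Transfusion independent, baseline hemoglobin below 10 g/dL.** A rise of at least 2 g/dL counts only if there was no PRBC transfusion in the prior 2 weeks and the rise was "without any erythropoietin, erythropoietin mimetics within the last 4 weeks prior to the increase in hemoglobin level" of that size.
- **Transfusion dependent.** Here "anemia response is defined as a period of at least 12 consecutive weeks without PRBC transfusion after the first dose of study drug", and the run must fall "on or prior to 30 days post last dose of study drug, the start of post-study treatment, disease progression or death, whichever occurs earlier". Erythropoietin is not mentioned.

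SAP 8.5.1.7 repeats the difference. In Table 6 the transfusion-independent response date carries the erythropoietin condition, while the transfusion-dependent date is "On the first date observing no PRBC transfusion for at least 12 weeks". Table 7, which covers transfusion-independent subjects only, lists as a loss of response the "use of any erythropoietin, erythropoietin mimetics within 30 days of last dose of study drug". Duration for transfusion-dependent subjects is simply the first PRBC-free period of at least 84 days.

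SAP 8.4.1.2 reports the rate for all evaluable subjects together and also by baseline transfusion status.

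Protocol 5.2.4 states: "Treatment with supportive medications for MF such as interferon, erythropoietin, danazol, and steroids, is not permitted during study drug treatment". Protocol Appendix E (Table 9 footnote) requires, for transfusion-dependent subjects, "absence of any PRBC transfusions during any consecutive 'rolling' 12-week interval during the treatment phase". SAP Appendix B carries the same footnote.

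**The concern.** The SAP treats erythropoietin as a confounder in one stratum and is silent about it in the other, without giving a reason. Protocol 3.6 itself lists "erythropoiesis-stimulating agents, androgens or immunomodulatory agents for anemia" among conventional treatments, so this is a drug class expected to reduce transfusion need. The secondary objective is the anemia response rate associated with navitoclax, alone or with ruxolitinib. If a transfusion-dependent subject can count as a responder with erythropoietin support, the combined rate mixes two definitions, and the two strata cannot be compared on the same footing.

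**Working it through.** **Plan's own figures.** The plan gives no figure for anemia response. Its precision table (SAP Table 1) uses the Clopper-Pearson interval that SAP 8.4.2 also assigns to this endpoint. Recomputing all 12 rows reproduces them to two decimals, for example 16/34 = 47.06% (29.78 to 64.87). The same routine is used below.

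**Step 1: can erythropoietin enter a counted run?**

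- *On drug.* Protocol 5.2.4 prohibits it, so use is a deviation. SAP Appendix A tabulates subjects who took prohibited medication, but nothing in 8.4.1.2 changes their response status. The run still counts.
- *After last dose.* The prohibition is tied to study drug treatment, so it has lapsed. The SAP window stays open for up to 30 days unless post-study treatment, progression or death comes first.
- *Does the post-study-treatment cutoff catch it?* SAP 8.1 defines post-study treatment as systemic therapies for myelofibrosis, radiation or transplant, and does not say whether erythropoietin belongs there. Protocol 5.2.4 classes it as supportive medication. Table 7 names erythropoietin as an event and, separately, uses the start of post-study treatment for censoring. The cutoff cannot be assumed to cover it.

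**Step 2: how much of the run can lie after last dose?**

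- Required run: 12 × 7 = 84 days.
- Maximum post-dose days: 30.
- Minimum days up to last dose: 84 − 30 = 54, and 54/84 = 64.3%.
- Maximum post-dose share: 30/84 = 35.7%.

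A subject who is PRBC-free for the last 54 days on drug and then receives erythropoietin for 30 days off drug meets the rule as written. A subject with fewer than 54 such days cannot be carried over by the tail.

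**Step 3: is the tail always available?** No. Under SAP 6.4, ruxolitinib given after the last navitoclax dose in Cohorts 1a and 1b is post-study treatment, which can close the window early. Those cohorts hold about 34 + 80 = 114 of the 174 subjects.

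**Step 4: effect of one reclassified responder.** The documents do not give the number of transfusion-dependent subjects, so the sizes below are assumptions. The table shows 3 responders falling to 2.

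| Assumed transfusion-dependent n | 3 responders (95% CI) | 2 responders (95% CI) | Change (1/n) |
|---|---|---|---|
| 5 | 60.0% (14.7 to 94.7) | 40.0% (5.3 to 85.3) | 20.0 points |
| 10 | 30.0% (6.7 to 65.2) | 20.0% (2.5 to 55.6) | 10.0 points |
| 15 | 20.0% (4.3 to 48.1) | 13.3% (1.7 to 40.5) | 6.7 points |
| 20 | 15.0% (3.2 to 37.9) | 10.0% (1.2 to 31.7) | 5.0 points |

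The combined rate moves less, because its denominator also includes transfusion-independent subjects with hemoglobin below 10 g/dL.

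**The case against.** The strongest defence has four parts.

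1. **The transfusion-dependent rule follows the published criteria as reproduced.** Protocol Appendix E and SAP Appendix B contain no erythropoietin condition for either group, so the clause for transfusion-independent subjects is an addition by the SAP. This is true, but having decided that erythropoietin confounds the endpoint, the SAP needs a reason to apply that in one stratum only. It gives none.
2. **The protocol prohibits use on drug, and the tail is short.** Both are true, and both limit the size. Neither removes the gap, because deviations do not alter response status and the prohibition ends with study drug.
3. **Thirty days after last dose is the SAP's usual window** for adverse events and transfusion endpoints. That makes it a reasonable convention, so the case for a treatment-phase restriction is only as a sensitivity analysis.
4. **Impact is unquantified.** This stands. Nothing in the documents shows how many subjects would be affected.

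A reader might also infer three stronger points that the documents do not support.

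- *That danazol, steroids and time off drug favour only the transfusion-dependent stratum.* Neither rule mentions androgens or steroids, and hemoglobin values up to 30 days after last treatment also count for transfusion-independent subjects. Only erythropoietin is handled differently.
- *That Appendix E requires the run to end by last dose.* It refers to the treatment phase, which Protocol 5.1 defines as first dose through the Treatment Completion Visit. Protocol 5.4.1 foresees that this visit may fall 30 or more days after last navitoclax.
- *That off-drug erythropoietin can generate a response by itself.* Step 2 of the working rules this out.

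**Conclusion.** The point holds as an inconsistency within one secondary endpoint. Erythropoietin or mimetic use disqualifies a transfusion-independent response and ends it, but has no effect on a transfusion-dependent response, and the two are pooled. As written, the rule can count a response that was partly supported by erythropoietin.

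The size is bounded but not known. At most 30 of 84 days (36%) can come from the post-dose window, possibly fewer in Cohorts 1a and 1b. On-drug use requires a protocol deviation. With an assumed 5 to 15 transfusion-dependent subjects in a cohort, each reclassified responder moves that stratum's rate by 20 to 6.7 points, well inside its confidence interval. The off-drug route also assumes that erythropoietin is not recorded as post-study systemic therapy for myelofibrosis.

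The endpoint is estimated without formal testing. The primary endpoint and the sample size are unaffected. It should be corrected because the correction is cheap, not because a material bias has been shown.

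**What to change.** - **SAP 8.4.1.2 and Table 6:** for transfusion-dependent subjects, require no erythropoietin or mimetic within 4 weeks before, or at any time during, the 12-week PRBC-free interval. A subject with another interval that meets the condition would still qualify.
- **SAP 8.5.1.7:** make such use end the transfusion-dependent response, as Table 7 already does for transfusion-independent subjects.
- **Sensitivity analysis:** restrict the 12-week interval to the protocol's treatment phase, from first dose through the Treatment Completion Visit.
- **Optional:** an exclusion for androgens, or for steroids given for myelofibrosis. If adopted, it should apply to both strata.

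The cost is SAP wording and programming. Protocol 5.3.1.1 already has medications recorded from screening until 30 days after last dose. The reported anemia response rate may fall slightly. Plain 12-week transfusion independence remains available as a separate endpoint in SAP 8.5.1.6, so no information is lost.

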6.1.4 Adverse Event Collection Period

All adverse events reported from the time of study drug administration until 30 days, following discontinuation of navitoclax administration have elapsed will be collected, whether solicited or spontaneously reported by the subject. In addition, protocol-related serious adverse events and protocol-related non-serious adverse events will be collected from the time the subject signed the study-specific informed consent.

Adverse event information will be collected as shown in Figure 2.

Figure 2. Adverse Event Collection

* Only if considered by the Investigator to be causally related to study-required procedures.

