# 4.0 Analysis Populations

[figure not shown]
In this study, study treatment is navitoclax + ruxolitinib (Cohort 1a, 1b and 3) or navitoclax alone (Cohort 2). Unless otherwise noted, study drug refers to navitoclax and ruxolitinib for combination therapy (Cohort 1a, 1b, and 3); and navitoclax for mono therapy (Cohort 2). Cohort 1 refers to Cohort 1a and Cohort 1b together.

The following sets will be used for analyses:

Full Analysis Set (FAS) includes all enrolled subjects who received at least one dose of navitoclax. The FAS will be used for all demographic/baseline analyses. Unless otherwise specified, the FAS is also the analysis population for the primary and the secondary endpoints.

The Safety Analysis Set includes all enrolled subjects who received at least one dose of navitoclax. The safety analysis set will be used for all safety analyses, unless otherwise specified.

The pharmacokinetics (PK) analysis set includes all the enrolled subjects who received at least one dose of navitoclax and have at least one post-dose PK assay results. The PK set will be used for PK analyses.

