## 6.4 Dose intensity (DI) and Relative Dose Intensity (RDI)

An observed dose intensity (ODI) will be derived for each subject who receives the study drug based on how it was actually administered. A planned dose intensity (PDI) will also be derived based on the protocol-specified schedule of the study drug.

For ODI it is calculated as:

[figure not shown]
ODI = 
$$\frac{\text{Actual total dose}}{\text{Actual total duration of treatment exposure (days)}}$$

For PDI it is calculated as:

PDI 
$$=$$
  $\frac{\text{Planned total dose over protocol specified}}{\text{Actual total duration of treatment exposure (days)}}$ 

RDI is defined as: RDI =  $(ODI/PDI) \times 100\%$ .

The RDI will be summarized based on the study drug administration form in EDC. Ruxolitinib administered before the first dose of navitoclax is considered as prior study treatment therapy collected in the Study Cancer Prior Systemic Therapies (Myelofibrosis)

form in EDC for Cohort 1 (Cohorts 1a and 1b). Ruxolitinib administered after the last dose of navitoclax for Cohort 1 (Cohorts 1a and 1b) is considered as post-study treatment collected in Post Study Drug Systemic Therapies form in EDC.

The actual total duration of treatment exposure in the above equations is defined as the last dose date minus first dose date + 1 for navitoclax or ruxolitinib, respectively. Descriptive statistics will be presented for navitoclax (for all Cohorts) and ruxolitinib (for Cohort 3, Cohort 1a and Cohort 1b) respectively.

Number and percentage of subjects who have dose reductions or interruptions, will be summarized.

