#### Definition of First Date of and Last Date of Study Treatment

First date of study treatment is the date of the first dose of navitoclax. Last date of study treatment is the date of the last dose of navitoclax.

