#### 8.5.1.6 Post Baseline Red Blood Cell Transfusion

Post Baseline Red Blood Cell transfusion (for any reason) evaluation period is from after the first dose of study drug to earliest day of on or before the last dose of study drug + 30 days, or the start of post-study treatment.

Post baseline transfusion independent rate will be calculated as the proportion of subjects who achieved PRBC transfusion independent during the treatment period. PRBC Transfusion independent is defined as a period of at least 12 weeks (≥ 84 days) with no PRBC transfusions during the evaluation period. In addition, the rate of conversion will be calculated as proportion of subjects being post-baseline PRBC transfusion independent from baseline PRBC transfusion dependent.

The duration of PRBC transfusion independent will also be summarized for overall and by transfusion status at baseline (transfusion dependent and transfusion independent). The duration of transfusion independence is defined as the first time period that a subject received no PRBC transfusions for at least 12 weeks ( $\geq$  84 days). The descriptive

statistics (median and range) will be provided for the duration of transfusion independence.

Incidence rate of PRBC transfusion/subject/month, defined as total number of PRBC transfusion from all subjects divided by total duration of treatment from all subjects (months).

Time from first date of study treatment to the first time receiving 2 or more units of PRBC transfusion will be summarized.

Above endpoints will be analyzed in the Full Analysis Set.

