# 9.2.1 Treatment-Emergent Adverse Events

[figure not shown]
Treatment-emergent AEs (TEAE) are defined as any AE with the onset that is on or after the first dose of navitoclax until 30 days after the last date of study drug. Events where the onset date is the same as the study drug start date are assumed to be treatment emergent. If an incomplete or missing onset date was collected for an AE, the AE will be assumed to be treatment-emergent unless there is evidence to the contrary (e.g., the AE end date was prior to the date of the first dose of study drug). All TEAEs will be summarized overall, as well as by primary MedDRA SOC and PT. The SOCs will be presented in alphabetical order, and the PTs will be presented in alphabetical order within each SOC.

The number and percentage of subjects experiencing TEAEs will be summarized.

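### SAP 8.4.1.2 ends the anemia-response window on two different drugs, so a transfusion-dependent Cohort 3 subject can be credited for time on ruxolitinib alone

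*SAP*

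**What the plan says.** Anemia response is a secondary endpoint with one rule for each baseline transfusion status (SAP 8.4.1.2).

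- **Transfusion independent, hemoglobin below 10 g/dL.** Hemoglobin values are ignored once 30 days have passed since the last date of study treatment. SAP 7.1 fixes that date: "Last date of study treatment is the date of the last dose of navitoclax".
- **Transfusion dependent.** The 12 transfusion-free weeks must fall "after the first dose of study drug and on or prior to 30 days post last dose of study drug", or before post-study treatment, progression or death if one of these comes first.

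SAP 4.0 states that, unless otherwise noted, "study drug refers to navitoclax and ruxolitinib for combination therapy", meaning Cohorts 1a, 1b and 3. Nothing in 8.4.1.2 notes otherwise.

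Post-baseline transfusion independence (SAP 8.5.1.6) uses the same anchor. Its period runs "to earliest day of on or before the last dose of study drug + 30 days", or to the start of post-study treatment.

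SAP 6.4 adds that ruxolitinib taken after the last navitoclax dose in Cohorts 1a and 1b "is considered as post-study treatment collected in Post Study Drug Systemic Therapies form in EDC". No matching sentence covers Cohort 3.

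The treatment-emergent window in SAP 9.2.1 covers events "on or after the first dose of navitoclax until 30 days after the last date of study drug". Protocol 6.1.4 sets collection by navitoclax: adverse events within 30 days "following discontinuation of navitoclax administration have elapsed will be collected".

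**The concern.** The two rules feed one response rate but can end on different dates. In Cohorts 1a and 1b, ruxolitinib continued after navitoclax counts as post-study treatment and closes the window. In Cohort 3 no text closes it for that reason. A programmer who follows SAP 4.0 would keep the window open until 30 days after the last ruxolitinib dose.

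A transfusion-dependent Cohort 3 subject who stopped navitoclax could then complete the 12 transfusion-free weeks mostly or wholly off navitoclax and still count as a responder. A transfusion-independent subject in the same position could not be credited for a late hemoglobin rise. The reported rate would combine two different windows, and any error from the longer one goes towards a higher rate.

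**Working it through.** The plan gives no figure for this window, so there is none to reproduce. The Clopper-Pearson calculation used in step 4 does reproduce SAP Table 1 for n = 30 (12/30: 22.66 to 59.40).

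**1. Anchors side by side**

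| Place | End of window | Drug that sets it |
|---|---|---|
| SAP 8.4.1.2, transfusion independent | last date of study treatment + 30 days | navitoclax (7.1) |
| SAP 8.4.1.2, transfusion dependent | last dose of study drug + 30 days | navitoclax or ruxolitinib, whichever is later (4.0) |
| SAP 8.5.1.6 | last dose of study drug + 30 days | same |
| SAP 8.5.1.7 | study treatment in the text, both terms in Table 7 | mixed |
| SAP 9.2.5.3, transfusion requirements | last navitoclax dose + 30 days | navitoclax, by name |

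**2. Can ruxolitinib outlast navitoclax in Cohort 3?** The documents allow for it. SAP 5.0 tabulates discontinuation of each drug separately. Protocol 5.1 (Follow-Up) mentions continued ruxolitinib in Cohorts 1a, 1b and 3.

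**3. Day arithmetic.** Let day 0 be the last navitoclax dose, t the day of the last PRBC transfusion and R the last ruxolitinib day. Assume no 84-day run was completed earlier and no other event has closed the window. The run ends on day t + 84.

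- Navitoclax anchor: credited if t + 84 ≤ 30, that is t ≤ −54.
- Study-drug anchor: credited if t + 84 ≤ R + 30, that is R ≥ t + 54.
- Days of the run after day 30: t + 84 − 30 = t + 54, for t from −54 to 30.

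| t | Run ends | Navitoclax anchor | Ruxolitinib needed to day | Days of run after day 30 |
|---|---|---|---|---|
| −54 | 30 | credited | none | 0 |
| −30 | 54 | not credited | 24 | 24 |
| 0 | 84 | not credited | 54 | 54 |
| 30 | 114 | not credited | 84 | 84 |

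Moving the end date later keeps every run already completed, so the responder count can rise but not fall.

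Day 30 matters because of recording. Protocol Table 6 marks transfusion status through the treatment completion visit and the 30-day safety visit, and leaves it blank in post-treatment follow-up. If the completion visit follows navitoclax discontinuation, scheduled recording ends near day 30 and the last column counts unrecorded days. If that visit waits until ruxolitinib stops, those days are recorded but are still off navitoclax.

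**4. Size.** The number of transfusion-dependent subjects in Cohort 3 (about 30 subjects) is not given. Assume 3, 6 or 9. One reclassified subject moves the stratum rate by 1/3 = 33.3, 1/6 = 16.7 or 1/9 = 11.1 points. With 6, going from 1 to 2 responders changes 16.7% (95% CI 0.4 to 64.1) to 33.3% (4.3 to 77.7). In the 8.5.1.6 rate over all 30 subjects, one subject is 1/30 = 3.3 points.

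**The case against.** **Recording.** The strongest reply is that the extra time may not be both open and unrecorded. If Cohort 3 ruxolitinib continues as study drug, treatment visits should continue and transfusions are recorded at them. If the completion visit has passed, later ruxolitinib may be entered as post-study systemic therapy, which under SAP 8.1 is post-study treatment in any cohort and closes the window. This largely stands. Protocol 5.4.1 ties the safety visit to the last navitoclax dose, while Protocol 5.1 ties it to the completion visit, so the documents do not settle which case applies. A reader might infer that transfusions go unrecorded after navitoclax and that silence is scored as transfusion-free. The SAP does not say so, and recording runs about 30 days past navitoclax in either case.

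**Reach of SAP 6.4.** The Cohort 1 sentence sits in the dose-intensity section and does not say that Cohort 3 differs. Protocol 5.1 names all three cohorts together. That makes the Cohort 3 position ambiguous, but it does not supply the missing rule.

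**Other closures.** Progression (which includes relapse under SAP 8.1), death or other therapy also ends the transfusion-dependent window, so a subject who stops navitoclax for failure may already be closed out. This stands for 8.4.1.2. Section 8.5.1.6 lists only post-study treatment.

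**Large illustrations.** At an assumed 0.25 transfusions per week, the chance of an 84-day gap is about 6% in 90 days and about 43% in 330 days. A reader might take that as the size of the bias. It mainly shows that longer windows yield more gaps, and longer navitoclax treatment would do the same.

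**Regimen-based window.** Ruxolitinib starts on Day 1 in Cohort 3 as part of the regimen, so a window covering either drug is a defensible choice. It would then have to apply to both rules, and the SAP does not do that.

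**Conclusion.** The inconsistency is in the text. One secondary endpoint has two end-of-window anchors. On the SAP's own definitions, the transfusion-dependent window in Cohort 3 stays open on ruxolitinib alone unless progression, death or other post-study therapy closes it. The direction is certain: the longer window can only raise the response rate and the transfusion-independence rate.

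The size is conditional. It needs a Cohort 3 subject who is transfusion dependent, stops navitoclax, stays on ruxolitinib recorded as study drug, and has no closing event. The documents do not say how many such subjects there are. With 3 to 9 transfusion-dependent subjects assumed, each one reclassified is worth 33 to 11 points in that stratum.

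The documents do not support the stronger statement that the Cohort 3 rate is in fact biased by unrecorded transfusions. For a subject last transfused on the stop date, up to 54 of the 84 days may be unrecorded, depending on when the completion visit takes place. Cohorts 1a and 1b are protected by SAP 6.4. The analysis is descriptive, with no formal test, so the consequence is a misstated estimate rather than a wrong test decision. The mismatch in the adverse-event window is the same in kind, but little effect is expected because collection itself stops 30 days after navitoclax.

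**What to change.** - In the transfusion-dependent paragraph of SAP 8.4.1.2, in 8.5.1.6 and in 8.5.1.7 (including Table 7), replace the last dose of study drug with the last dose of navitoclax, as 9.2.5.3 already does.
- In the same places, end the window no later than the subject's last transfusion-status assessment. No credit is then given for days without recording, whenever the completion visit took place.
- Use the navitoclax anchor for the end of the treatment-emergent window in 9.2.1, to match Protocol 6.1.4.

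The cost is SAP wording and the matching end-date derivation in the programs. It needs no new data and no change to study conduct.
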